## 7. Rationale and Background

Psoriasis is a systemic autoimmune condition affected by genetic and environmental factors [2]. Approximately 30-50% of psoriasis patients develop psoriasis before the age of 20. In Europe and North America, the prevalence of psoriasis among paediatric patients ranges between 1.3-2.1% with an estimated incidence rate of 40.8/100,000 person-years [3-5]. Several reports indicate that the incidence of paediatric psoriasis has been increasing over time from 29.6/100,000 person-years in 1974 to 62.7/100,000 person-years in 1995 [4, 6]. The median age of onset among paediatric psoriasis patients is between 7 and 10 years [4]. The hallmark of plaque psoriasis is plaques (patches) of inflamed, red skin covered with silvery scales. Approximately 80-90% of psoriasis patients have the plaque form of psoriasis, causing itching and pain, most typically involving skin of the scalp, trunk, buttocks, and limbs [7]. Psoriatic arthritis is one of the most common coexisting conditions, as about 30-40% of psoriasis cases also develop psoriatic arthritis [8, 9].

Paediatric onset psoriasis differs from its adult counterpart as pharyngitis, stress, and trauma are more common triggers of disease activity [4]. Upper respiratory infections appear to be the most common trigger for the onset of paediatric plaque psoriasis, but other environmental triggers such as trauma, drug exposure, and physical or psychological stress have been linked to paediatric onset also.

There are currently no international guidelines for the medical treatment of paediatric psoriasis, only published case reports and/or series. This has complicated the management of psoriasis systemic therapy among moderate-to-severe paediatric patients. Thus, most of the systemic treatments for paediatric psoriasis are off-label and based on established guidelines for adults with psoriasis [10]. The United States (US) based paediatric guidelines highlight the use of biologic medications indicated for other conditions as effective treatment for moderate-to-severe paediatric psoriasis [11]. Although earlier publications point to the primary goal in the treatment of childhood psoriasis as effective control of disease, more recent work suggests a more aggressive approach. Currently, etanercept, adalimumab, ustekinumab, and ixekizumab are the only biologics approved for use in the United States and the European Union for the moderate-to-severe paediatric psoriasis populations. Secukinumab has been approved for paediatric plaque psoriasis use in the EU but not in the US. Topical therapies or phototherapy are more widely used, but are likely not as effective in treating moderate-to-severe psoriasis among paediatric patients [10].

Ixekizumab is a humanised IgG4 monoclonal antibody that binds with the IL-17A cytokine. It is currently approved in the US and Europe for moderate-to-severe plaque psoriasis in paediatric patients aged 6 to less than 18 years of age. Ixekizumab is administered once monthly as a subcutaneous injection, with the paediatric dosage depending on the child's weight. Investigation concerning the effects of ixekizumab on moderate-to-severe paediatric plaque psoriasis is currently limited to one randomised, double-blind, placebo-controlled trial among children (N=182). Results demonstrate that ixekizumab improves both pathologic skin features and clinical symptoms of chronic moderate-to-severe plaque psoriasis. However, there is some concern that by blocking IL-17-mediated chemokine production, ixekizumab may increase susceptibility to infections [12]. Additional long-term safety studies are necessary to confirm these findings.

## 8. Research Question and Objectives

The objectives of this study are to monitor the uptake of ixekizumab in a real-world paediatric psoriasis population, to characterise the demographic and clinical characteristics of paediatric patients receiving ixekizumab and appropriate comparator medications, and to obtain information about the long-term safety pertaining to serious infections and inflammatory bowel disease.

The null hypothesis is that incidence of SI and IBD are similar in paediatric psoriasis patients exposed to ixekizumab compared to paediatric populations unexposed to ixekizumab.

## 9. Research Methods

### 9.1. Study design

This cohort study uses US administrative health care data from the HealthCore Integrated Research Database (HIRD). It will take place in two phases as described below.

### 9.2. Phase 1: Uptake Monitoring

During the uptake monitoring phase, children between the ages of 6 to less than 18 with exposure to ixekizumab or appropriate comparator medications will be identified and characterised with respect to demographics and clinical characteristics. Surveillance for serious infections (SI) and inflammatory bowel disease (IBD) will be performed, and measures of disease occurrence (numbers, percentages, and incidence rates) will be presented in annual reports. These outcomes will be validated via medical record review for the interim and final study reports.

Uptake monitoring is expected to continue for the duration of the study to ensure identification of ixekizumab-exposed patients. The results of this phase of the study will determine the feasibility for initiation of a comparative analysis (Phase 2) and determine the need to include additional data sources, extend the study timeline, or both (see Section 9.8).

### 9.3. Phase 2: Comparative Safety Analysis

The purpose of Phase 2 is to conduct comparative analyses to assess the association between ixekizumab exposure and the occurrence of SIs and IBD. The informativeness of comparative analyses depend on the number of patients available to analyse and the number of outcomes observed. Therefore, this phase of the study will depend on the results of Phase 1. If a sufficient number of exposures are identified, a formal comparative analysis will be conducted where we will calculate unadjusted and propensity score adjusted incidence rates (IR) and incidence rate ratios (IRR), with applicable 95% confidence intervals (CI) as appropriate for each individual outcome (Section 9.10).

### 9.4. Setting

The study population will include children (6 to less than 18 years of age) within a large, US administrative insurance claims database diagnosed with plaque psoriasis and exposed to ixekizumab or comparator medications: biologic medication (etanercept), non-biologic systemic medication (acitretin, cyclosporine, and methotrexate), and non-systemic topical treatment (corticosteroids, calcipotriene). If ixekizumab is approved for additional paediatric indications (e.g., psoriatic arthritis) during the study period, the study population will be expanded to include the new indications.

### 9.5. Inclusion and exclusion criteria

#### Inclusion Criteria

To be eligible for this study a patient must meet the following inclusion criteria:

- Age 6 to less than 18 years at the first dispensing of ixekizumab or comparator drug
- At least one diagnosis of plaque psoriasis before first dispensing of study medication

- At least one claim for ixekizumab or a comparator medication
- At least six months of continuous health plan eligibility before first dispensing of the study medication (first users of each medication).

### Exclusion Criteria

Children will be excluded if they meet any of the following criteria:

- Children diagnosed during the baseline period with a disease listed below for which one or more of the drugs in this study is indicated:
  - Polyarticular juvenile idiopathic arthritis
  - Psoriatic arthritis
  - Ankylosing spondylitis
  - Ichthyoses
- Children who have history of an organ transplant.

## 9.6. Variables

### 9.6.1. Exposures

Defining exposure episodes for the primary and sensitivity analyses will depend on use of these medications in routine clinical practice. Therefore, preliminary work evaluating drug utilisation will be conducted before finalising exposure episodes. Exposure to ixekizumab or comparator medications will be identified from outpatient pharmacy claims using National Drug Codes (NDC), Generic Product Identifier (GPI), or drug administration procedure codes (e.g., Healthcare Common Procedure Coding System [HCPCS]), as applicable. Detailed information on ixekizumab and other medications used during the study period will be obtained, including dates of prescription/administration, dose, and duration of treatment.

Treatment episodes will be initiated by the first dispensing or administration of the study drug or comparator plus the number of days of supply/dosing interval and continue through five half-lives after the last dispensing or administration of the drug. If there is a gap between administrations/days' supply of the drug that is greater than five half-lives, that time will not be included in the exposed time period. However, the final definition of the treatment episode for the primary analysis will depend on use of these medications in routine clinical practice. Therefore, preliminary work evaluating drug utilisation will be done prior to finalising exposure episode. Additional detail regarding the definition of treatment episodes and management of treatment switching during the study period will be provided in the statistical analysis plan (SAP).

### Drug of interest

- Ixekizumab

### Comparator drugs

- Biologic
  - Etanercept

Like ixekizumab, etanercept is a biologic medication which was first approved in the US in 1998 and the EU in 2000, with approvals for paediatric psoriasis in the US in 2016 and in the EU in

2009. Etanercept is commonly used among children >6 years old with moderate-to-severe plaque psoriasis. Although ustekinumab and adalimumab are also approved to treat children with psoriasis in the US and EU, they are also indicated to treat IBD and therefore are not considered as comparators for this study. Recently, secukinumab has been indicated for moderate-to-severe paediatric plaque psoriasis in Europe but has not been approved by the Food and Drug Administration (FDA) and thus will not be included in our study.

### Non-Biologic Systemics

- Acitretin
- Cyclosporine
- Methotrexate

### Non-Systemic Topicals

- Corticosteroids
- Calcipotriene

Non-biologic drugs are commonly used for children with paediatric plaque psoriasis. These include acitretin, a non-immunosuppressing retinoid, and the immunosuppressants methotrexate and cyclosporine. None of these are FDA approved for psoriasis in children because of the lack of randomised controlled trials in this age category. Therefore, data on the risks and benefits of these non-biologic therapies come from long-term use in paediatric patients for conditions such as ichthyoses (acitretin), juvenile rheumatoid arthritis (methotrexate) and organ transplantation (cyclosporine) [10, 12]. A retrospective study using data from 2000 to 2014 found that among children with moderate-to-severe psoriasis, acitretin was the most frequently used therapy [13]. Non-systemic topicals are widely prescribed for mild cases of paediatric plaque psoriasis.

### 9.6.2. Outcomes

The study outcomes are serious infection and inflammatory bowel disease. In Phase 1, administrative claims data will be used to identify potential outcomes based on International Classification of Diseases, Tenth Revision (ICD-10) diagnosis and procedure, Common Procedural Terminology, and HCPCS codes. The codes and algorithms that will be used to identify the outcomes will be detailed in a separate SAP. Outcomes will be validated for the interim and final reports.

- Serious infection will be classified as follows:
  - Affected body system (e.g., respiratory tract, gastrointestinal tract, urinary tract, etc.)
  - Infections related to an injury or burn will not be included; the algorithm required to differentiate these injuries will be highlighted in the SAP.
- Inflammatory bowel disease will be identified from diagnoses of ulcerative colitis (UC) or Crohn's disease (CD) in a clinic, office, or hospital setting.

IBD is an episodic condition, thus we will categorise a diagnosis as 'new onset' if the child did not have any claims for IBD during the baseline period. If the child had a claim for IBD during the baseline period and another after a dispensation of a study treatment, this second diagnosis would be characterised as an 'exacerbation' of IBD. However, it is possible that a child could

have been diagnosed with IBD before entering our database and thus, it is possible that we may misclassify an exacerbation of IBD as a new case.

### 9.6.3. Covariates

Demographic and clinical information for patients including medical history, comorbidities, pre-existing medical conditions potentially related to increased risk of SI/IBD, and prior and concomitant medications will be examined. Plaque psoriasis and other relevant medical conditions are captured using the ICD-10 coding system as obtained from inpatient and outpatient medical claims. The use of medications before ixekizumab dispensing which may be markers for the presence or the severity of comorbid illness will be assessed. Prior use of medications for chronic medical conditions will be examined. Information on use of medications prescribed for the treatment of plaque psoriasis, and other chronic medical conditions will be extracted.

Baseline characteristics and demographic information will include:

- Demographic characteristics
  - Age (years)
  - US region of residence
  - Duration of health plan eligibility prior to dispensing
  - Calendar year of entry into the study
- Clinical characteristics
  - Autoimmune and inflammatory immune conditions
    - Plaque psoriasis
    - Lupus
    - Multiple sclerosis
    - Alopecia areata
    - Inflammatory bowel disease
  - Diabetes
  - Obesity
  - Hypertension
  - Depression
  - 10 most frequently occurring diagnoses recorded (for descriptive analyses)
- Medication use
  - Other medication used to treat plaque psoriasis, excluding those mentioned in Section 9.6.1 (e.g., phototherapy, biologic, and non-biologic therapies)
  - Immunosuppressants
  - 10 most frequently occurring medications recorded (for descriptive analyses)
- Healthcare utilisation (separately within the 6 months prior to the study)
  - Count of any office visits, emergency department visits, visits to a gastroenterologist, and hospitalisations
- Ixekizumab and comparator drug treatment characterisation (during the study period)
  - Duration of exposure
  - Treatment lines (i.e., observed treatment sequences in claims)

- Distribution of prior plaque psoriasis treatments.

## 9.7. Data Sources

This study will be conducted by HealthCore using the HIRD, a large administrative healthcare database maintained by HealthCore for use in health outcomes and pharmacoepidemiologic research. The HIRD is a longitudinal medical and pharmacy claims database from health plan members across the US. Member enrolment, medical care (professional and facility claims), outpatient prescription drug use, outpatient laboratory tests, and healthcare utilisation may be tracked for health plan members in the database dating back to January 2006, and with diagnoses recorded in ICD-10 since October 2015. Medical records will be obtained to validate outcomes as described in Section 9.10.3.

If uptake monitoring suggests that the number of ixekizumab-exposed children identified in the HIRD is below expected numbers outlined in Section 9.8, additional data sources will be incorporated. Exploration of other potential data sources will begin after protocol approval. If this approach is ultimately required, the protocol will be amended.

## 9.8. Study Size

The available number of exposed children will depend on the uptake of ixekizumab in the US among children between the ages of 6-<18 years. Preliminary feasibility counts from the HIRD indicate that biologic medications (etanercept and ustekinumab) are not widely used in paediatric psoriasis populations. Over a four-year period (2015-2019), there were approximately 580 paediatric psoriasis patients treated with a biologic, which, if divided equally among two available medications with steady accrual over 4 years would correspond to ~70 ((580/4 years)/2 medications) patients per medication, per year. No requirements for continuous health plan eligibility or other inclusion criteria were made in obtaining these preliminary counts. Although there remains a significant unmet medical need in this population, the uptake of a single medication such as ixekizumab is expected to occur more slowly than previously available biologic treatments and be impacted by the introduction of new medications to the marketplace. Available sample size will also be reduced by the requirement for continuous health plan eligibility, which is needed to assess baseline patient characteristics. Additionally, preliminary feasibility counts from the HIRD (2015-2019) indicate that non-biologic (N=2,551) and non-systemic medications (N>4,000) are more commonly prescribed in the paediatric population, allowing us to increase the ratio of comparator to ixekizumab for those two analyses. No requirements for continuous health plan eligibility or other inclusion criteria were made in obtaining these preliminary counts.

Assuming approximately 70 ixekizumab-exposed patients per year, this study will identify approximately 392 ixekizumab-exposed children from the time of the FDA paediatric indication approval (March 30, 2020) through the end of data collection (October 30, 2025). The lowest detectable relative risks with 80% power given a 1:1 etanercept:ixekizumab ratio for the study outcomes to be analyzed are described in Table 1. Table 1 also displays the lowest detectable relative risk with 80% power for estimated sample sizes given a 6:1 non-biologic comparator: ixekizumab and 9:1 non-systemic comparator: ixekizumab ratio for each of the study outcomes. All calculations assume a two-sided Type I error rate of 0.05 and baseline rates of serious infection and IBD in a paediatric population from the published literature [14, 15].

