### **Study size**

The available number of exposed children will depend on the uptake of ixekizumab in the US among children between the ages of 6 to <18. With 392 ixekizumab-treated children and 392 etanercept-treated children, the study will achieve 80% power to detect a 16.8-fold difference in the incidence of SI and a 3.9-fold difference in the incidence in new onset or exacerbations of IBD between ixekizumab and etanercept. Additionally, with 2,352 children prescribed systemic non-biologic treatments and 3,528 children prescribed only non-systemic treatments, the study will achieve 80% power with to detect at least an 8.9-fold difference in the incidence of SI and IBD between ixekizumab and systemic non-biologic treatment or non-systemic treatment. If we are not on track to accrue the targeted number of patients for an interim analysis by second quarter of 2023, we will reach out to additional data sources to determine the number of ixekizumab-exposed children that could be identified by expanding the study to include multiple databases, or consider extending the timeline of the study. Feasibility of continuing the study, either as a single database or a multi-database study, will be considered in consultation with regulatory authorities.

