**Table 1. Lowest Detectable Ixekizumab Relative Risk for Serious Infection and Inflammatory Bowel Disease**

Comparator	Comparator to Ixekizumab Ratio	Lowest Detectable Relative Risk with 80% Power c	
		Serious Infection a	IBD b
Etanercept N=392	1:1	3.94	16.8
Non-Biologic N=2,352	6:1	2.9	8.9
Non-systemic N=3,528	9:1	2.82	8.5

**Abbreviations:** IBD = inflammatory bowel disease; N = number.

a Estimated background incidence 1% (over a 5-year period) [14]

b Estimated background incidence 0.1% (over a 5-year period) [15]

c These values were calculated using EpiSheet [16]

An interim report will be produced for delivery to the EMA by October 30, 2023. That report will contain uptake monitoring information for all study drugs, validated outcomes, and demographic information for all children who have been accrued into the study. In the case that the desired sample sizes are not reached in the HIRD by the second quarter of 2023, we will evaluate the feasibility of expanding the study population using additional data sources. Available data on uptake of the study drug and counts of outcomes will be summarised and reported in the interim and final reports.

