## 9.10. Data Analysis

### 9.10.1. Primary Analysis

In Phase 1, the number of children with exposure to ixekizumab, comparator drugs, and incidence of SI and IBD will be calculated. All cases of SI and IBD will be submitted for medical adjudication by clinical specialists and results of the validation will be presented in the interim and final reports. In order to achieve our target size by October 2025, we will assess uptake of the ixekizumab and comparator drugs at the end of second quarter of 2023 and determine if additional data sources need to be incorporated into the study or if the timeline for uptake monitoring needs to be extended. No additional analysis is planned for Phase 1.

In Phase 2, we will describe the number and percentage of children in each cohort for all of the demographic, clinical, treatment, and utilisation characteristics described in Section 9.6.3. Applicable baseline characteristics will then be used to calculate an exposure propensity score (PS) by modelling the probability of ixekizumab exposure versus the etanercept, non-biologic drugs, and non-systemic drugs (separately) as a function of the covariates [17]. Propensity score

matching will be used to balance risk factors for SI or IBD among ixekizumab-treated patients and each of the comparison groups. We will create separate propensity scores for SI and IBD as the risk factors for these outcomes are different. Propensity score matching uses variables identified as potential risk factors in the baseline period before the first dispensing of the drug of interest (e.g., age, geographic region, current comorbidities, and calendar time) as predictors of the choice of therapy. Propensity score matching produces groups that have similar distributions of variables included in the PS as well as any variables strongly associated with these covariates.

For each outcome (Section 9.6.2), we will describe the IR (calculated as the number of events divided by the person-time at risk). Incidence rate ratios (IRR) and corresponding 95% CIs will be calculated comparing children exposed to ixekizumab to children exposed to etanercept, children treated with non-biologic prescription medications, and children treated with topicals.

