Another limitation of this study is the use of non-systemic topical treatments as a comparator group for a biologic medication indicated for children with moderate-to-severe paediatric plaque psoriasis. Patients prescribed non-systemic topical medication might be expected to have a milder form of the disease or not be appropriate candidates for biologic medications due to other comorbidities. Thus, we expect reduced comparability between the children in the ixekizumab and non-systemic topicals groups. Any differences in disease severity and indications for the non-systemic topicals between treatment groups introduces potential confounding bias that must be considered when interpreting the results of this study.

The main limitations relate to uncertainties regarding the numbers of subjects available to study for a new medication, and limitations inherent in database studies, including accuracy of codes used to identify outcomes. Also, uptake of a new product (plus the follow-up time necessary to observe events) will determine the time at which a sufficient study size for analysis will be accrued in the database, as discussed in Section 9.8. Additionally, the sample size for this study was calculated based on the number of children in the HIRD (between 2015-2019) with moderate-to-severe plaque psoriasis who were prescribed biologic medications. Given the rare occurrence of moderate-to-severe paediatric plaque psoriasis requiring biologic medications, this study is planned for a sample size to detect a 16.8-fold difference in risk of IBD among children

prescribed ixekizumab versus etanercept. However, among children who were prescribed non-biologics as compared to those prescribed ixekizumab, the study will have the sample size to detect  $\geq 8.9$ -fold increase in risk for IBD. Furthermore, because SI is more prevalent than IBD, the planned sample size will allow us to detect a  $\geq 3.9$ -fold difference in risk for SI among children who were prescribed ixekizumab, compared to those who were prescribed etanercept.

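### Table 1's 80% power is a large-sample figure that fails at the event counts its inputs imply: for IBD versus etanercept, with 0.39 expected comparator events, exact power at 16.8-fold is 53%

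*Protocol*

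**What the plan says.** Protocol Section 9.8 projects uptake at about 70 children a year, so that "this study will identify approximately 392 ixekizumab-exposed children" by the end of data collection. It then gives "The lowest detectable relative risks with 80% power given a 1:1 etanercept:ixekizumab ratio" in Table 1, and larger comparator groups at 6:1 (non-biologic, 2,352) and 9:1 (non-systemic, 3,528). It adds that "All calculations assume a two-sided Type I error rate of 0.05". The table's footnotes set a five-year background of 1% for serious infection (SI) and 0.1% for IBD, and say "These values were calculated using EpiSheet". No test is named and no expected event count is given.

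The abstract makes an 80% power claim for the same groups ("With 392 ixekizumab-treated children and 392 etanercept-treated children"), though it attaches the two etanercept figures to the opposite outcomes. Section 9.12 says "this study is planned for a sample size to detect a 16.8-fold difference in risk of IBD among children" prescribed ixekizumab versus etanercept.

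For the analysis, Section 9.10.1 describes the incidence rate for each outcome and says "Incidence rate ratios (IRR) and corresponding 95% CIs will be calculated comparing children exposed to ixekizumab to children exposed to etanercept", and likewise for the other two comparators. Section 9.3 also plans unadjusted and propensity-score-adjusted rates and ratios, with 95% intervals where applicable.

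**The concern.** A background of 0.1% in 392 children is less than half an event. A normal approximation to how events split between two groups is unreliable there, and it errs in the favourable direction: a conventional exact test needs more events to reject than the formula supposes. If so, the 80% is overstated on the protocol's own inputs, before any loss of follow-up.

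Two things are at stake. Reaching the target number of children is what opens the comparative phase, and a shortfall prompts a search for further databases or a longer timeline, so the detectable risk printed beside that target informs a feasibility decision in a safety study requested by a regulator. Also, the only comparative measure planned is a ratio. A ratio with an empty comparator cell has no finite point estimate, and a null IBD result read against a stated 80% power would look more reassuring than it is.

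**Working it through.** **Inputs (Section 9.8 and Table 1).** 392 ixekizumab children; k = 1, 6 or 9 comparator children for each; background p0 = 1% (SI) or 0.1% (IBD); two-sided 0.05. Every child is credited with the full five-year risk, as the table does.

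**Reproducing the stated figure.** Expected events are m0 = 392·k·p0 (comparator) and m1 = 392·p0·RR (ixekizumab). Put M = m0 + m1, P = 1/(1+k), p = m1/M. The approximation is

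power = Φ{[m1 − M·P − 1.96·√(M·P(1−P))] / √(M·p(1−p))}.

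For IBD versus etanercept at 16.8: m0 = 0.392, m1 = 6.586, M = 6.978, P = 0.5, p = 0.944. The numerator is 6.586 − 3.489 − 1.96 × 1.321 = 0.508 and the denominator is 0.608, so power = Φ(0.836) = 79.8%. The same formula returns the whole table, so the table contains no arithmetic slip.

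**Exact power, same cell.** With 1:1 allocation and no effect, each event falls in either group with probability 1/2. With 0 etanercept events, 5 ixekizumab events give p = 0.0625 and 6 give p = 0.031. Rejection therefore needs at least 6 against 0, 8 against 1, or 10 against 2. With Poisson counts of mean 0.392 and 6.586:

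- P(0 etanercept) × P(≥6 ixekizumab) = 0.676 × 0.643 = 0.435
- P(1) × P(≥8) = 0.265 × 0.340 = 0.090
- P(2) × P(≥10) = 0.052 × 0.130 = 0.007

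The sum is 53%. Fisher's exact test also gives 53%.

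**Dependence on the test, same cell.**

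| Test | Ixekizumab events needed against 0 | Power at 16.8 |
|---|---|---|
| Exact conditional | 6 | 53% |
| Mid-P | 5 | 67% |
| Uncorrected score | 4 | 75% |
| Likelihood ratio | 3 (2 × 3 × ln 2 = 4.16 > 3.84) | 84% |

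**All cells.** Where a range is shown, the lower value doubles the smaller tail and the higher uses the minimum-likelihood two-sided p-value; at 1:1 they agree.

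| Comparison | Table 1 RR | Approximation | Expected events, comparator / ixekizumab | Exact power |
|---|---|---|---|---|
| IBD, etanercept | 16.8 | 16.83 | 0.39 / 6.59 | 53% |
| IBD, non-biologic | 8.9 | 8.90 | 2.35 / 3.49 | 59–65% |
| IBD, non-systemic | 8.5 | 8.48 | 3.53 / 3.33 | 54–64% |
| SI, etanercept | 3.94 | 3.97 | 3.92 / 15.4 | 71% |
| SI, non-biologic | 2.9 | 2.90 | 23.5 / 11.4 | 69–75% |
| SI, non-systemic | 2.82 | 2.83 | 35.3 / 11.1 | 70–75% |

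Fisher's test with binomial counts gives SI values up to 76%. An uncorrected score test brings SI to about 78–80%, so the SI shortfall is modest.

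**Relative risks with 80% exact power (minimum-likelihood).** IBD: about 23, 11.5 and 11. SI: about 4.4, 3.1 and 3.0. With mid-P, IBD versus etanercept needs about 20.

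**Empty comparator cell, IBD.** Etanercept: exp(−0.392) = 0.68. Non-biologic: exp(−2.352) = 0.095. Non-systemic: exp(−3.528) = 0.029. Under no effect, neither the ixekizumab nor the etanercept group has an event with probability exp(−0.784) = 0.46.

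**The case against.** The protocol names no test, and the choice matters. The exact conditional test is very conservative here: under no effect at this background it rejects less than once in 10,000. A likelihood-ratio test reaches 84% with a true error rate of about 1%. So a reader might infer that the 80% fails under any test, and that is not so. The defence is confined to this one cell: the same test gives 68–70% for the other two IBD comparisons, and its error rate can exceed 0.05 for SI. It also declares 3 events against 0 significant, where the exact p-value is 0.25.

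A reader might also infer that the study would give no usable IBD answer, or that the ratio generally has a zero denominator. The protocol does not support either. Incidence rates are planned alongside the ratios, the empty-cell problem is specific to etanercept, and 6 events against 0 still gives a finite lower limit and a significant test.

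The sparse data are partly acknowledged. The 392 is projected uptake rather than a number solved from power, Phase 2 is conditional on patients and outcomes observed, extra data sources are foreseen, and Section 9.12 lists 16.8-fold as a limitation. That stands, but Section 9.12 presents 16.8-fold as what the study can detect and mentions no shortfall.

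The IBD outcome also counts exacerbations, and prior IBD is not an exclusion, so true counts may differ from those at 0.1%. That figure is nevertheless the protocol's own for this outcome. Interval methods may properly sit in the SAP, which is not at hand, but an exact interval there would not restore the 80% printed here.

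**Conclusion.** The point holds for the power statement. On Table 1's own inputs, 80% power at 16.8-fold is not delivered by an exact, mid-P or score test. The other two IBD cells fall short under exact, mid-P, score and likelihood-ratio tests alike; the SI cells fall short by less. For IBD versus etanercept, and only there, the most likely result (probability 0.68) is a ratio without a finite point estimate.

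These figures assume independent events at the stated background and five full years of risk for every child. The second assumption is generous. If accrual were uniform from 30 March 2020 and every child were followed without discontinuation to 30 October 2025, mean follow-up would be 5.58/2 = 2.79 years. Expected etanercept events would then be 0.392 × 2.79/5 = 0.219, and the chance of none exp(−0.219) = 0.80. The protocol does not give 2.79 years. It is an upper-end assumption, because exposed time stops five half-lives after the last dispensing.

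No sample size or eligibility rule changes. The message that only very large IBD effects are detectable becomes stronger.

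**What to change.** In Section 9.8, show expected events per group in Table 1, name the test, and replace the entries with exact or mid-P detectable relative risks (exact minimum-likelihood: IBD about 23, 11.5 and 11; SI about 4.4, 3.1 and 3.0). Alternatively, keep the present values and print the power they actually carry. Bring the abstract and Section 9.12 into line, including which figure belongs to which outcome in the abstract.

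In Section 9.10.1, or in the SAP by reference, specify exact or mid-P intervals for the rate ratio and for the ixekizumab incidence rate that is already planned. Say what is reported when a comparator has no events. Add the incidence rate difference with an interval that stays defined at zero. As an illustration under the upper-end follow-up assumption, 0 events in 392 × 2.79 ≈ 1,094 person-years gives an upper 97.5% limit of 3.69/1,094 = 3.4 per 1,000 person-years; shorter follow-up widens it.

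The cost is a few lines of text and minor programming. The drawback is that the published detectable risks look less favourable.
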